Pauls Stradiņš Clinical University Hospital plus up to 10 additional sites

CRO:

Institute of Science, Pauls Stradiņš Clinical University Hospital

Study Sponsor:

Pauls Stradiņš Clinical University Hospital with a grant from the TBA.

I. BACKGROUND

Coronary artery disease (CAD) is the primary cause of morbidity and mortality in patients with carotid artery disease. Patients with asymptomatic carotid stenosis have a four-fold higher risk of myocardial infarction (MI) than stroke¹ and the presence of carotid stenosis is an independent predictor of cardiac death.^{2,3} Patients undergoing carotid endarterectomy (CEA) have a higher risk of myocardial infarction (MI) than stroke and those with post-op MI have a 5 year survival of only 56%.⁴ Despite this high cardiac risk and the knowledge that 60% of carotid endarterectomy patients have coronary angiographic evidence of significant CAD (>70% stenosis),⁵ systematic pre-operative cardiac testing is not recommended for vascular surgery patients since randomized trials have shown no long-term survival benefit from pre-operative coronary revascularization.⁶ Guidelines specifically note that cardiac testing should not be performed in patients with no coronary symptoms⁷ and thus most patients undergo major vascular surgery without pre-operative cardiac testing and mortality of patients with post-op MI remains high despite evidence-based medical therapy.⁸

Myocardial ischemia is common in patients with CAD, is often asymptomatic (silent), and is a marker for adverse cardiac events and reduced survival.⁹ Pre-operative non-invasive testing of patients undergoing carotid or peripheral vascular surgery showed that 25-40% of patients had silent ischemia and that silent ischemia was a predictor of adverse outcomes.¹⁰⁻¹² While cardiac stress testing provides valuable information on myocardial perfusion, it does not provide actionable information regarding coronary artery lesions which may be producing ischemia and which may benefit from revascularization. The ischemic potential of a coronary stenosis can be determined at the time of coronary angiography by measurement of fractional flow reserve (FFR). Randomized trials of patients with stable CAD and lesion-specific coronary ischemia as demonstrated by $FFR \leq 0.80$ in at least one large coronary artery have shown that FFR-guided coronary revascularization results in a significant reduction in death/MI at 5 years compared to medical therapy.^{13,14}

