A newly introduced non-invasive diagnostic modality, coronary CT-derived fractional flow reserve (FFR_{CT}) provides a unified anatomic and functional assessment of coronary artery disease which can reliably identify ischemia-producing coronary lesions.¹⁵ FFR_{CT} analysis is based on anatomic information provided by coronary CTA with computational analysis of coronary blood flow to provide fractional flow values throughout the coronary tree. FFR_{CT} accurately reflects invasively measured FFR¹⁶ and can help guide patient management decisions.^{17,18} The clinical usefulness of FFR_{CT} is well documented¹⁹ and FFR_{CT} analysis is now being used in the US, Europe, Canada and Japan to evaluate stable patients with symptoms of CAD. The usefulness of FFR_{CT} in evaluation of patients without cardiac symptoms is unknown.

In a prospective, single-center, observational study of patients with no known CAD undergoing CEA, a strategy of pre-operative cardiac evaluation using coronary CTA and FFRCT, along with ischemia-guided coronary revascularization following CEA, resulted in a more than 50% reduction in all-cause

death, cardiac death, myocardial infarction, and MACE, with improved 5-year survival compared to patients receiving standard cardiac evaluation and care (84% vs 64%, $p < .001$)²⁰⁻²¹.

The purpose of this study is to determine the prevalence of silent coronary ischemia in patients undergoing carotid revascularization (endarterectomy or stenting) using coronary CTA and FFR_{CT} and to evaluate the potential usefulness of FFR_{CT} in selecting patients for coronary revascularization to reduce cardiac events and improve survival.

II. OBJECTIVE

The primary objective of this study is to determine whether among symptomatic and asymptomatic CAS patients with no known CAD who had undergone carotid artery revascularization (endarterectomy or stenting) a strategy of best medical therapy (BMT) plus selective coronary revascularization based on FFR_{CT} assessment of lesion-specific coronary ischemia can reduce adverse cardiac events and improve survival compared to BMT alone. Lesion-specific coronary ischemia is defined as FFR_{CT} ≤ 0.80 distal to stenosis in a major (≥ 2 mm) coronary artery with severe ischemia defined as FFR_{CT} ≤ 0.75 .

III. STUDY ENDPOINTS

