The primary endpoint of the study is a composite of cardiac death, myocardial infarction (MI) or urgent (unplanned) coronary revascularisation (MACE) during 2 years follow up. Secondary endpoints include cardiac death, MI, urgent coronary revascularisation, cardiovascular (CV) death, all-cause death during follow up.

IV. STUDY DESIGN

This study targets a population of patients with symptomatic or asymptomatic carotid artery stenosis (CAS) (symptomatic to asymptomatic in 1:1 ratio) and no prior cardiac history, no myocardial infarction, no coronary angiography or coronary CTA, and no coronary revascularization (PCI or CABG) who have undergone successful carotid artery revascularisation with planned post-operative best medical therapy. Within 14 days following carotid revascularisation, patients will be randomly assigned to BMT alone or BMT plus coronary CT angiography (which must be completed within 14 days of randomization) and FFR_{CT} analysis to determine the functional significance of coronary lesions identified on the CT scan. Results of the CT scan and FFR_{CT} analysis in patients randomized to the CT-FFR_{CT} group, will be provided to treating physicians to help guide patient management with Vascular Heart Team consideration for coronary angiography and revascularization as appropriate for each patient. Coronary revascularisation (PCI or CABG), if indicated, is strongly recommended within 3 months from the randomisation. Clinical follow up (based on date of randomization) is planned 6 months, one and 2 years. Additional long-term follow up out to 5-years is planned for participating centers. An independent academic clinical events committee will adjudicate all endpoints in a blinded manner. The definition of outcome events will be in

accordance with Academic Research Consortium-2 consensus document²². Sample size power calculations assumed a hazard ratio of 0.5 with estimated sample size up to 300 patients (up to 150 in each group), 90% power, alpha .05. The patient sample size may be reduced if statistical significance been achieved.

V. INCLUSION AND EXCLUSION CRITERIA

Inclusion Criteria

1. Inform consent obtained before any study-related activities
2. Age above or equal to 50 years with symptomatic or asymptomatic critical carotid stenosis (symptomatic patients with at least Rankin III.) which has been successfully revascularized by carotid endarterectomy or stenting within the past 14 days

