3. Willing and able to undergo coronary CTA scan within 14 days of randomization and agrees to submission of CTA data set for HeartFlow FFRct analysis with results made available to treating physician

Exclusion Criteria

1. Known CAD, history of MI, prior coronary revascularization (PCI or CABG)
2. Patient underwent coronary angiography or coronary CTA before the randomization
3. Known history of 2nd or 3rd degree heart block; sick sinus syndrome; long QT syndrome
4. History of severe asthma, severe or bronchodilator-dependent COPD
5. Severe congestive heart failure (NYHA III or IV)
6. Severe arrhythmia, prior pacemaker or internal defibrillator lead implantation
7. Impaired chronic renal function (EPI-GFR \leq 30ml/min)
8. Subjects with known anaphylactic allergy to iodinated contrast
9. Pregnancy or unknown pregnancy status in subject of childbearing potential
10. Evidence of ongoing or active clinical instability, including acute chest pain (sudden onset), cardiogenic shock, unstable blood pressure with systolic blood pressure <90 mmHg, or acute pulmonary edema
11. Any active, serious, life-threatening disease with a life expectancy of less than 2 years
12. Any active infection
13. Inability to comply with study procedures
14. Contraindication for guideline-guided longterm antiplatelet/anticoagulation regime after PCI/CABG
15. Large neurologic deficit (Rankin scale $>III$)

16. Participation in any interventional clinical study within 30 days prior to screening

VI. Rules for subject withdrawal and terminating the study

In accordance with the Declaration of Helsinki, as amended, each subject is free to withdraw from the study at any time. Investigator(s) also have the right to withdraw subjects from the study in the event of illness, adverse events (AEs), serious adverse events (SAEs), other reasons concerning the health or well being of the subject, or in the case of lack of cooperation. The reason for withdrawal must be noted in the Case Report Forms (CRFs). If the reason for withdrawal is a clinical AE or SAE, follow up of the subject will continue until the outcome is evident. The specific event or test result(s) must be recorded in the CRFs.

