a by a combination of 7 additive dose reduction strategies: ECG dose modulation; Weight-based tube voltage; Prospective ECG triggering; Minimization of "padding"; Minimization of Z-axis coverage; Limiting of the field of view (FOV); Automatic exposure control. Coronary CTA performance necessitates the use of iodinated contrast. Minor reactions to x-ray contrast material can occur, including itches or hives with an incidence of approximately 1 in 200 subjects. More severe reactions that are very infrequent include hypotension, laryngospasm and bronchospasm. The incidence of these reactions is estimated at about 1 in 5,000 and is treated with intravenous epinephrine. Extravasation of x-ray contrast material outside the vein during injection may occur and result in a painful soft tissue swelling and bruising. Subjects will be monitored for extravasation during injection and the amount of contrast material injected into the tissues is usually quite small without significant clinical consequences.

VIII.B. Risks of FFR_{CT} analysis

In subjects with Coronary CTA, FFR_{CT} analysis will be performed using the clinically acquired Coronary CTA data set. The FFR_{CT} analysis in these subjects does not require additional imaging, medication or radiation exposure. There is no additional risk to the subject.

IX. STUDY PROTOCOL REQUIREMENTS

1. After providing informed consent, each subject will undergo the following assessments as indicated on CRF:
 - a. Collection of demographic information, including height, weight, presenting symptoms and neurologic status.
 - b. A summary of index carotid revascularization procedure
 - c. A summary of the subject's relevant medical and surgical history (Diabetes mellitus, Dyslipidemia, Arterial hypertension, Smoking)
 - d. Recording of concurrent and concomitant medications
2. Coronary CTA (cCTA) Procedure
 - . 1) Perform cCTA with strict adherence to SCCT guidelines including, but not limited to:
 - a. Heart rate control: administration of β -blockers, if needed, to achieve a heart rate of <60 bpm
 - b. CT image acquisition after administration of sublingual nitrate spray or after administration of sublingual nitrate tablet (3-5 minutes)
 - c. using breath-holding and other techniques to minimize motion artifact
 - d. contrast protocols: bi-phasic injection protocol
 - e. kV/mA settings per ALARA principles. Patients who weigh more than 70kg should be scanned at 120kV.

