 - 2) The additional thorax CT findings (pulmonary oncology, etc.) might be collected at selected sites.

3. Post-procedure follow up data from clinical visits and/or phone calls 3 months, one and 2 years (annually up to 5 years for patients entering prolonged study at participating sites).
4. Open label randomization will be done after patient screening at approximate rate 1:1 symptomatic to asymptomatic CAS.

X. Case Report Forms

Electronic or paper case report forms will be used.

XI. Institutional Review

Before starting this study, the protocol will be submitted to the regulatory bodies/local health authorities (in accordance with local regulations) and the study will not start before the EC/IRB gives written approval or a favorable opinion in accordance with ICH E6-GCP and all applicable regulatory bodies/local health authorities give approval or a favorable opinion as required.

XII. Informed consent

Written and oral information about the study in a language understandable by the subject will be given to all subjects by the investigator and/or designee. The subject's willingness to participate in the study will be documented in writing in a consent form, which will be signed by the subject with the date of that signature indicated. The investigators will keep the original consent forms and copies will be given to the subjects. The informed consent will also be signed and dated by the person who conducted the informed consent discussion.

XIII Confidentiality regarding study subjects

The investigator(s) must assure that the privacy of the subjects, including their personal identity and all other personal medical information, will be maintained at all times. In documents or image material submitted to the sponsor, subjects will not be identified by their names, but by an identification code. Personal medical information may be scrutinized for the purpose of verifying data recorded in the CRF. This may be done by properly authorized persons, the quality assurance unit, or regulatory authorities. Personal medical information will always be treated as confidential.

XIV Financial Disclosure

The investigator(s) (or investigating institution) will provide the sponsor with accurate financial disclosure regarding real or potential financial conflicts of interest.

XV Insurance

As there is no any invasive investigation product been tested, the local site clinical liability insurance will be in power to cover malpractice.

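### Inclusion 2 sets Rankin III as a minimum for symptomatic patients and exclusion 15 sets it as a maximum, so read literally only one grade is eligible

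*Protocol*

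**What the plan says.** Three parts of the protocol bear on this point.

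- **Eligibility (section V).** Inclusion 2 covers patients aged 50 or over with critical carotid stenosis and adds, for symptomatic patients only, "symptomatic patients with at least Rankin III.) which has been successfully revascularized by carotid endarterectomy or stenting within the past 14 days". Exclusion 15 applies to all patients and removes those with "Large neurologic deficit (Rankin scale $>III".
- **Population (sections II and IV).** The primary objective is posed "among symptomatic and asymptomatic CAS patients with no known CAD who had undergone carotid artery revascularization". The design section fixes the mix as "symptomatic to asymptomatic in 1:1 ratio", and section IX item 4 repeats it: "Open label randomization will be done after patient screening at approximate rate 1:1 symptomatic to asymptomatic CAS". None of these statements mentions a minimum level of disability.
- **Assessment (section IX, item 1a).** After consent the protocol calls for "Collection of demographic information, including height, weight, presenting symptoms and neurologic status". It names neither the Rankin scale nor the time to which the neurologic status refers.

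**The concern.** Inclusion 2 gives symptomatic patients a floor, and exclusion 15 gives everyone a ceiling at the same grade. A floor on disability also runs against the evident purpose of exclusion 15, which is to keep out patients with a severe deficit. The protocol gives no reason for barring the least disabled symptomatic patients.

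This is a screening rule, so whatever it says determines who is enrolled, and an analysis plan cannot repair that afterwards. A site that follows the text recruits a different symptomatic population from the one in the objective. A site that guesses at the intent recruits patients whom a monitor could classify as ineligible, and section VI lists serious protocol violations among the grounds for terminating a centre. With the lead hospital "plus up to 10 additional sites", the phrase could be applied in more than one way within the same trial.

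**Working it through.** The protocol states no figure that depends on this rule, so there is nothing to reproduce. The check is set logic on the two criteria.

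**Inputs**

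- Inclusion 2, literal: symptomatic patients need grade ≥ III.
- Exclusion 15: grade > III is excluded, so grade ≤ III remains.
- Direction of the scale: exclusion 15 treats grades above III as a large deficit, so higher means worse.
- Sample size (section IV): up to 300 patients, up to 150 per group.
- Symptomatic to asymptomatic ratio (sections IV and IX): about 1:1.
- Assumption: the protocol does not list the grades, so the scale is taken to start either at 0 or at I. The grades exclusion 15 tolerates are then 0 to III (four) or I to III (three).

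**Reading A: literal, both criteria on the same assessment.** {≥ III} and not {> III} = {III}. This admits 1 of 4 tolerated grades, or 1 of 3. The single-grade result does not depend on where the scale starts; only the denominator does.

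**Reading B: literal, with inclusion 2 referring to presentation and exclusion 15 to screening.** A patient must have presented at III or above and be at III or below at screening. The single-grade result no longer follows. Of the grades exclusion 15 tolerates, those below III at presentation are still barred: 3 of 4, or 2 of 3.

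**Reading C: the bracket means no worse than III.** {≤ III} and not {> III} = {≤ III}. All tolerated grades are admitted, 4 of 4 or 3 of 3. The two criteria agree, and the bracket adds nothing to exclusion 15.

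| Reading | Tolerated grades admitted (scale from 0) | Tolerated grades admitted (scale from I) | Matches the stated population? |
|---|---|---|---|
| A | 1 of 4 | 1 of 3 | No |
| B (grade at presentation) | 1 of 4 | 1 of 3 | No |
| C | 4 of 4 | 3 of 3 | Yes, within exclusion 15 |

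Under B, patients who presented above III can also qualify if they are at III or below by screening; the table counts only the tolerated grades.

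**Share of the trial governed by the rule.** 300 × 1/2 = 150 symptomatic patients at most, and 150 / 2 = 75 per arm if symptom status is balanced between arms. Both are approximate, because the ratio is approximate and 300 is an upper limit. Sites: 1 + up to 10 = up to 11.

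These numbers show the reach of the rule. They do not count patients wrongly excluded, which would need a Rankin distribution that the protocol does not give.

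**The case against.** The best defence is that reading C is what was meant. Exclusion 15 names the problem it guards against, the document describes itself as a working draft, and its English is loose elsewhere. On that reading eligibility is unaffected and the fault is one redundant phrase. This is a fair account of the probable intent. It does not make the text adequate, because screening staff apply the criterion as written and nothing in the protocol directs them to reading C.

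A second argument is that an objective is a summary which eligibility criteria then narrow. The objective also omits the age, renal and heart-failure limits, and nobody would call those contradictions. That is right: a narrower criterion is not by itself an inconsistency. Nor are the two criteria strictly incompatible, since grade III satisfies both. What remains is that the literal result confines about half the trial to one grade, with no rationale anywhere and against the direction of exclusion 15.

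Third, the case report form is not shown and may name the scale and the time point, and screening is the natural default for judging eligibility. This also stands: the missing time point would not be a finding alone. It matters here because it leaves reading B open, and under B the patients who presented with milder grades are still barred.

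Finally, grade fractions count labels on a scale and not patients, and 150 is an enrolment target and not a loss. Both points are accepted, and the figures are offered as context only.

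**Conclusion.** The concern holds: inclusion 2 is wrong as written. Taken literally on one assessment, it and exclusion 15 leave Rankin III as the only eligible grade for symptomatic patients, whereas the objective and design name symptomatic patients with no such floor. The only reading that restores agreement is one the text does not express.

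The conclusion rests on the wording of the two criteria and on the direction of the scale that exclusion 15 implies. It needs no assumption about where the scale starts. The single-grade result does assume that both criteria refer to the same assessment; if they do not, the exclusion of milder presentations remains.

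The rule reaches up to about 150 of 300 patients. The recruitment loss cannot be computed. Because the rule applies before randomisation and equally to both arms, it does not bias the treatment comparison, and no endpoint or power figure is challenged. The effect is on the enrolled population, consistency between sites and generalisability. It should be fixed, but it does not threaten the trial's internal validity.

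**What to change.** Before screening, the sponsor should reconcile inclusion 2 with exclusion 15 and with the population named in sections II and IV. There are two ways to do so: delete the bracket in inclusion 2, so that exclusion 15 alone governs disability, or reword it so that both criteria express the same intended limit. Which limit is intended is for the sponsor to state; none is proposed here.

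The same correction should say when Rankin is graded (at presentation, or at screening after revascularisation), and the screening form should carry identical wording.

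The cost is one corrected phrase, one added sentence and an updated form, with no extra patients or procedures.

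### Section VI lets open-label investigators withdraw randomised patients from the study on health or cooperation grounds and does not keep them under outcome follow-up to 2 years

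*Protocol*

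**What the plan says.** Protocol Section VI lets patients leave at any time and then gives a separate right to the investigator: "Investigator(s) also have the right to withdraw subjects from the study in the event of illness, adverse events (AEs), serious adverse events (SAEs"), and further "other reasons concerning the health or well being of the subject, or in the case of lack of cooperation". On what happens next it has two rules. One concerns documentation: "The reason for withdrawal must be noted in the Case Report Forms (CRFs"). The other concerns follow-up: "If the reason for withdrawal is a clinical AE or SAE, follow up of the subject will continue until the outcome is evident".

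Section III makes MACE over 2 years the primary endpoint. The secondary endpoints include cardiac, cardiovascular and "all-cause death during follow up". Section IX, item 4, adds that "Open label randomization will be done after patient screening". Section IV provides for a blinded events committee.

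The visit schedule appears twice. Section IV: "Clinical follow up (based on date of randomization) is planned 6 months, one and 2 years". Section IX, item 3: "Post-procedure follow up data from clinical visits and/or phone calls 3 months, one and 2 years". Neither says whether it applies to a patient who has been withdrawn.

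**The concern.** Stopping a study procedure and leaving the study are different things, and Section VI provides only for the second. Most of its grounds are health-related, so they are plausibly linked to the risk of a later cardiac event or death. A patient withdrawn on them before an event can drop out of 2-year MACE. A patient withdrawn after a non-fatal MI still counts for MACE, but a later death can be missed once that MI has resolved.

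The investigator can know the arm, and the arms offer unequal occasions for withdrawal. Only the CTA arm must complete a scan within 14 days of randomisation and may go on to Heart Team review and revascularisation. Not attending the scan could be read as non-cooperation, and that can happen in one arm only.

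Equal loss in both arms costs power. Loss mainly in one arm also moves the hazard ratio, in either direction.

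**Working it through.** **1. What follow-up is stated for each ground in Section VI**

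| Ground for investigator withdrawal | Follow-up stated afterwards |
|---|---|
| AE or SAE | Until the outcome of that event is evident |
| Illness | None stated, unless it is also classed as a clinical AE |
| Other health or well-being reasons | None stated |
| Lack of cooperation | None stated |

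No row reaches 2 years, and none mentions MACE or vital status.

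**2. Events needed**

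Inputs from Section IV: HR 0.5, power 90%, alpha 0.05, up to 150 per group. The sidedness of alpha is not stated; I take two-sided.

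- Schoenfeld, 1:1: 4 × (1.960 + 1.282)² / (ln 0.5)² = 87.5, so 88 events.
- The planned 300 patients cannot be reproduced, because no control event rate, accrual pattern or dropout is given. For 300 patients to yield 88 events the pooled 2-year risk must be 88/300 = 29.3%.

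**3. Equal loss in both arms**

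Power = Φ(√d/2 × 0.693 − 1.960), where d is the number of events observed.

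| Events observed | Events lost | Power |
|---|---|---|
| 88 | 0 | 90.2% |
| 83 | 5 | 88.4% |
| 78 | 10 | 86.5% |
| 70 | 18 | 82.6% |

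**4. Loss in one arm only (illustration)**

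Assumptions, none of them in the protocol:

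- 150 patients per arm and 88 expected events with full follow-up.
- 20% of patients (30 per arm) have three times the hazard of the rest.
- Half, or a quarter, of these high-risk patients are withdrawn at a time uniform over the first 6 months, in one arm only.
- Their follow-up is censored at withdrawal.

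With HR 0.5 within each risk group, solving for 88 events gives a base hazard of 0.179 per year. That yields 55.9 control events (55.9/150 = 37%) and 32.1 CTA-arm events (32.1/150 = 21%). Half of 30 is 15; allowing for those who have an event first, about 13 to 14 of 150 are actually withdrawn. For a quarter it is about 7.

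| Scenario | Control + CTA events | Observed rate ratio |
|---|---|---|
| Full follow-up | 55.9 + 32.1 | 0.515 |
| Half withdrawn, CTA arm | 55.9 + 26.9 | 0.465 |
| Half withdrawn, control arm | 47.8 + 32.1 | 0.564 |
| A quarter withdrawn, CTA arm | | 0.491 |
| A quarter withdrawn, control arm | | 0.538 |
| One third withdrawn in both arms | 79.1 in total | 0.512 |

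The full-follow-up ratio is 0.515 rather than 0.5 because it averages over the two risk groups.

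**5. False-positive rate under no effect**

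Same set-up, 37% risk in both arms, two-sided log-rank test, 8,000 simulated trials per scenario:

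| Scenario | Rejection rate |
|---|---|
| No withdrawal | 5.1% |
| Half withdrawn, CTA arm | 7.0% |
| Half withdrawn, control arm | 7.5% |
| A quarter withdrawn, CTA arm | 5.6% |
| A quarter withdrawn, control arm | 5.5% |

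**6. A harsher variant**

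Suppose the events are missed but the patients still count as at risk. The apparent HR is then the true HR × (1 − hidden share). Under no effect, with 44 events per arm:

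- 10% hidden in the CTA arm: ln 0.90 / √(1/44 + 1/39.6) = −0.48, rejection 7.7%.
- 20% hidden in the CTA arm: ln 0.80 / √(1/44 + 1/35.2) = −0.99, rejection 16.7%.

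**The case against.** The strongest reply is that this is common permissive wording and the harm is inferred from silence.

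- **Nothing requires withdrawal, and Section IV plans 2-year follow-up for the trial population.** True, but Section IV does not say it applies after withdrawal, whereas Section VI does set a shorter horizon for AE and SAE cases. Read together, they do not secure the 2-year outcome.
- **Exposure is limited.** The study-specific procedure is one early scan with possible revascularisation, there is no long-term study drug, and patients unable to comply or with life expectancy under 2 years are excluded at entry. This stands and argues for modest expectations of how often the right will be used.
- **Some grounds are themselves endpoints.** If the SAE is an MI or an urgent revascularisation, the primary endpoint has already been met. This also stands; it narrows the loss for MACE but not for later death.
- **The illustration is built to show bias.** It puts all withdrawal in one arm, among the highest-risk fifth, early on. That is fair, and even so the shift is moderate. Equal withdrawal barely moves the ratio (0.515 to 0.512).
- **The consent form may cover data collection after withdrawal, and the analysis plan may set censoring and missing-data rules.** Possibly. An analysis plan cannot collect outcomes, and consent that permits collection does not oblige a site to do it.
- **Adjudication is blinded.** The committee can judge only the events it is sent.

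**Conclusion.** The concern holds. As written, Section VI permits health-related withdrawal from the study, decided with knowledge of the arm, and secures neither 2-year MACE nor vital status afterwards. That reading rests on the text and is firm.

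The size is not known, because the protocol gives no expected withdrawal rate, and no direction of bias can be claimed. Under the stated assumptions, even loss of 5 to 18 of 88 events lowers power from 90% to between 88% and 83%. One-arm loss of about 7 to 14 of 150 patients moves the rate ratio by roughly 0.02 to 0.05 and puts the false-positive rate at about 5.5% to 7.5%. It would be higher if missed events were counted as event-free follow-up. The effect is modest unless withdrawal is common and unbalanced. The change should still be made, because uncollected outcomes cannot be recovered later.

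The conflict between the two visit schedules (6 months against 3 months, and randomisation against an undefined procedure as the starting point) is real, but it is minor and separate. Both schedules include 1 and 2 years, and the main conclusion does not depend on it.

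**What to change.** In Section VI, separate stopping study procedures from leaving follow-up:

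- State that illness, AEs, SAEs, other health reasons or lack of cooperation may end study procedures but not outcome follow-up.
- Follow every randomised patient for MACE and vital status to 2 years from randomisation, unless the patient withdraws consent to follow-up.
- Keep the existing sentence on AE and SAE withdrawals only as the rule for following the individual event.

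Separately, reconcile the schedules in Sections IV and IX, item 3, into one set of visits with one starting point for both arms.

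The cost is protocol wording in Sections IV, VI and IX, and a check that the consent form agrees. Section IX already allows phone contact, so the added work is some extra calls or record checks for patients who stop procedures.
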